#### Field Observations

This study will use field observations to provide additional, complementary information on implementation of the HIV self-testing intervention (and control condition). Field observations are a well-established data collection technique in qualitative research that involve the presence of a researcher in a naturalistic setting, the witnessing of events and activities of interest, and often some degree of participation [81]. Observations provide a direct view of the event under study and thus complement the mediated perspective obtained through IDIs. [name] has been using field observations with success in her qualitative HIV research in sub-Saharan Africa for the past several years. The qualitative component of this study will include 20 observations of interactions between pregnant women and providers in PMTCT B+ clinic visits where HIV self-testing kits or letters of invitation to test are distributed. Field observations will be conducted by a Ugandan qualitative RA, trained and experienced in this approach to qualitative data collection. Observations will be conducted until 20 observations have been completed. Each observation session will last 2-3 hours. To minimize bias in collecting observational data, dates of observations will be randomly selected. Verbal consent is obtained to conduct observations, which is done by the Ugandan RA. Observations are recorded as field notes, which do not contain identifying information and serve as formal records for analysis.

#### Focus Group Discussions

Female and male participants will be asked to join focus group discussions designed for the study staff to gather feedback on how they can best support participants during their study involvement. Participants will sign a separate consent form before joining the focus group discussions. We will use FGDs for qualitative data collection, including understanding the major issues related to HIV self-testing and status disclosure, assessing variation in testing and disclosure experiences, eliciting attitudes and beliefs and understanding differences between participants.

#### Qualitative data quality and management

Data in the form of interview transcripts and field notes will be continuously reviewed for content, clarity, detail, and grammar by [name] research group. Feedback on quality and suggestions for improvement will be provided to the RA through regular supervision. Upon completion, transcripts and field notes will be routed electronically to Boston, using a secure file transfer system. Data will be stored on secure servers at the Harvard Medical School and at IDI Kasangati.

#### Qualitative data analysis

The goal of the qualitative analysis is to assess the acceptability of HIV self-testing and PrEP for male partners to pregnant women in PMTCT B+ and to male partners. The construct of acceptability is broadly defined to target not only participants' feelings and attitudes toward the intervention, but also their broader experiences with intervention components. The qualitative analysis will address "how" and "why" questions about intervention dynamics to inform future dissemination and intervention examples of questions to be answered through analysis of the qualitative data are:

- 1) When participating male partners completed an HIV test, what were the reasons?
- 2) When participating male partners did not test, what were the reasons?
- 3) In what ways, if any, did the availability of HIV self-testing kits influence the decision to test?

4) In what ways, if any, did receiving a letter of invitation influence men's decision to test?5) In what ways, if any, did self-testing or letters of invitation impact men's decisions for or against initiation of PrEP and/or ART, for male partners who tested for HIV?

We will use an inductive, content analytic approach [82] to data analysis, with coding and category construction as core analytic activities. The qualitative data set consists of up to 110 interview transcripts and 20 observation field notes. Analysis will begin with open-coding through review of 20% of the data to identify sections of text suggestive of acceptability. These sections of text will be labeled, defined, and illustrated to become codes, and assembled into a codebook. The codebook will be used for data coding, using the software program Atlas.ti to organize the coding process. Coding will be conducted by the Uganda RA and [name]. Data will be sorted by codes to identify themes corresponding to specific aspects of acceptability. The coded data will also be compared by code across groups to investigate systematic inter-group differences in perspectives of male partners, pregnant women and providers. Differences will be reported in descriptive categories. The final step in analysis is to develop descriptive categories. Categories will consist of a label, an operational definition and text specifying the category content, with illustrations through excerpts from interview transcripts or field notes. The categories will represent answers to the analytic questions specified above. Qualitative results will be compared with quantitative data on intervention acceptability collected as part of Aim 3. Qualitative data will be used to help interpret the results of the randomized trial.

#### DATA ANALYSIS

#### Sample size

Aim 1: The sample size was selected to ensure high power for the PrEP outcome as well as the male partner testing. Table 3shows a range of assumptions for the proportion of men who are HIV-uninfected (60-70%), and the test uptake in the standard of care arm (20-30%, as observed in MU-JHU's program) and Enhanced testing arms (55-66%).

proportion of				
HIV-negative men	on Prl	EP by arm (	(Aim 1)	
Proportion of	HIV t	est uptake	Sample size	e to achieve
HIV-negative	SOC	Enhanced	80% power	90% power
men				
60%	20%	55%	162	216
60%	20%	65%	103	138
60%	30%	55%	379	508
60%	30%	65%	203	271
70%	20%	55%	133	178
70%	20%	65%	84	112
70%	30%	55%	312	417
70%	30%	65%	165	221
Dondomization in (	1 for E	Theneady St		050/

## Table 3. Sample size calculations for comparison of proportion of

Randomization is 2:1 for Enhanced: SOC. Assumes 95% retention, 80% PrEP uptake

Assuming PrEP uptake in HIV-negative men is 80% and 60% of the men are HIV-uninfected, with a sample size of 500 we would have almost 90% power to detect an increase in PrEP use resulting from a change from 30% to 55% in test uptake. With 500 women, the power for assessing an increase in HIV test uptake exceeds 95% across a range of assumptions in Table 3.

Aim 2: Under the range of assumptions for HIV testing uptake in Aim 1, the overall HIV test uptake will be in the range 43-53% (Table 4) and the number of enrolled women with partners who test and begin ART or PrEP ranges from ~150-200. Assuming power for the causal inference can be approximated by logistic regression, we would have ~80% power to detect an OR of 1.75 or higher, assuming women have 50% ART continuation and viral suppression when male partners do not initiate PrEP or ART. If the number of women with partners who test is between 220-270, we would have approximately 85% power to detect an OR of 1.75.

Table 4. Power approximation for assessing impact of partner PrEP/ART use on women's viral suppression					
Overall HIV	HIV prevalence	HIV+ men on ART	Not on ART		

Overall HIV	HIV prevalence	HIV+ men on ART	Not on ART		
test uptake	in male partners	or HIV- men on	or PrEP		
		PrEP		OR=1.75	OR=2.0
43%	0.4	147	353	78%	92%
47%	0.3	166	334	81%	94%
50%	0.4	170	330	80%	94%
53%	0.3	189	311	83%	95%
Randomizatio	on is 2:1 for Enhance	ed: SOC. Assumes 95	% retention, 80	% PrEP upta	ke and

50% ART persistence

#### Outcome measurements

Aim 1: Women who are randomized will have key outcomes assessed at scheduled visits. The co-primary outcomes will be HIV testing by the male partner, as measured by questionnaires administered to women in clinic, and PrEP by 6 months after the woman initiated ART. The Kenya pilot indicated minimal bias in self-report of male partner testing. The secondary outcome is PrEP adherence among the male partners who initiate PrEP, based on detectable blood tenofovir levels at 3 and 6 months after PrEP initiation. PrEP use will also be measured by pharmacy records where men are dispensed PrEP (e.g.at the ANC or IDI Kasangati), and self-report through a validated 3-item questionnaire[83]. We will assess HIV seroconversion but expect a low rate.

Aim 2: The exposures of interest are male partner testing, PrEP initiation and ART initiation (Table 2). The primary outcome is the woman's viral load at 12 months post-partum. Viral suppression will be defined as plasma viral load <400 copies/ml). For the secondary outcomes, pharmacy records will be used to measure ART dispensation and women will be asked at quarterly visits about treatment interruptions[83]. Secondary outcomes include infant HIV status at 6 weeks (HIV-infected/uninfected) which will be ascertained from ANC records, and infant survival at 12 months as reported by the mother at her 12-month post-partum visit.

#### Capture of cohort clinical data

Data on male partner HIV testing and female partner ART use and viral load will be obtained from case report forms. Clinic and pharmacy records will be used to document PrEP prescriptions, abstracted in real time from pharmacy records to paper-based case report forms and entered into an electronic database. Automated legal range checks will be programmed to reduce data entry errors and internal quality control reports will be run monthly.

#### Statistical considerations

Aim 1: The primary analysis will be an intent to treat comparison by randomization arm of the primary outcome: the proportion of women whose male partners who test for HIV and the proportion of HIV-negative men who take PrEP within six months after their HIV-positive partner is randomized. The secondary outcome is tenofovir detection at 3 and 6 months among men who use PrEP.

Aim 2: Our primary analysis will assess the effect of male partner's PrEP or ART use on women's ART continuation and viral suppression at 12-month post-partum period, as the measure of her ART continuation and adherence. This intent of the analysis is to assess the impact of the male partner's current (time-dependent) PrEP or ART use on the women's current ART use and viral suppression. Since initiation of PrEP or ART is secondary to the randomized HIV testing intervention, causal inference methods will be used to assess the impact of male partner HIV testing and PrEP or ART use on post-partum ART continuation. We will calculate standardizedinverse-probability weights with logistic regression [84], to predict the probability of current male PrEP or ART use at each visit as predicted by the instrumental variable HIV testing randomization, and potential time-varying confounders (Table 3), including sexual behavior, future fertility desires, relationship power dynamics, intimate partner violence, alcohol use, and baseline demographics and duration of ART pre-partum. These weights will then be used in a pooled logistic regression model of partners' PrEP or ART exposure as predictors of: 1) ART continuation and 2) viral suppression. In a separate set of models, we will examine the direct effect of male testing, overall and separately for HIV-positive and HIV-negative men, on the woman's ART continuation and viral suppression. We will also explore an instrumental variables approach to causal estimation, given the expected role of randomization in male partners' initiation of PrEP and ART in Aim 1[85].

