2.1.2. Secondary Objectives

- Evaluate whether HIV testing combined with offer of PrEP for HIV-negative male partners and ART uptake for HIV-infected male partners increases effective post-partum ART use among HIV-infected Ugandan women in PMTCT B+.
- As a women's HIV disclosure to her partner is hypothesized to be the mechanism for increasing her effective ART use, we will evaluate associations between first visit a women reported disclosure of their HIV-infected status to their male partner and the trial endpoints: enrollment of the male partner, uptake of PrEP/ART; viral suppression. We will also assess whether male partner testing, HIV status and disclosure, impact trial endpoints.

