5.2.2. Use in analysis

Key predictors

- 1) Study arm: HIVST (Intervention arm) versus Letter (standard of care arm). Assigned at randomization of the women.

30 Sep 2021

- 2) Partner enrolled (time varying): whether male partner was enrolled prior to the current visit.
- 3) Uptake of PrEP/ART of partner (time varying):
 - a. A woman has a partner with PrEP/ART uptake at her visit if her partner knows his HIV status and is either on ART (if HIV-positive) or initiated PrEP (if HIV-negative) prior to that visit. Both male partners who do not enroll and male partners who do not initiate ART or PrEP are defined as no uptake of PrEP/ART. In analyses that use time to PrEP/ART, time of first report of PrEP/ART will be used.
 - b. An alternative definition will also define any HIV-negative men with partners who are virally suppressed as on PrEP/ART. A female partner is defined as being VS if she is virally suppressed at assessments both before and after the visit.
- 4) Disclosure of HIV-infected status to male partner self-reported at baseline

Effect modifiers:

- 1) Viral suppression of woman (time varying, measured at baseline, 6 and 12 mo)
- 2) Trimester of pregnancy at enrollment
- 3) Partner ever tested for HIV (time varying: reported by female partner)
- 4) Mutual disclosure status of HIV (time varying, as reported by each partner). If no enrolled male partner, mutual disclosure is assumed to not occur.
- 5) Male HIV status. If a male partner does not receive HIV testing from the study site, it is assumed their HIV status is unknown to both members of the coupleStudy Population

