7.2. Statement of the Null and Alternate Hypotheses

The null and alternative hypotheses are:

H_0 : Provision of self-test kits to the male partner by his pregnant partner does not have a differential effect on 1) male partner testing, 2) PrEP uptake in HIV-uninfected male partners or 3) viral suppression at 12 months in the women, compared to the standard of care (letter).

H_A : Provision of self-test kits to the male partner increases 1) male partner testing, 2) PrEP uptake in HIV-uninfected male partners and 3) viral suppression at 12 months in the women, compared to the standard of care (letter).

Subgroup Analyses

Subgroups of interest:

30 Sep 2021

- Women who have disclosed their HIV-infected status prior to/reported at baseline
- Women who were virally suppressed (VL < 50 copies/mL) at baseline
- Women <=24 vs > 24 years old
- Women who were on ARVs prior to their pregnancy

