Descriptive analysis:

- We will tabulate the number of women by the their partners disposition: 1) No partner enrolled 2) Partner enrolled, not initiated PrEP/ART, 3) partners enrolled and have initiated PrEP/ART. Baseline demographic and risk characteristics of women will be compared by group. If Group 2 is less than 10% of the cohort, it may be combined with Group 1.
- We will describe the characteristics of the women's viral load at 12 months within each group: mean, median, IQR, proportion with suppressed viral load.

Statistical analysis:

We will use modified Poisson regression with robust standard errors to compare the proportion of women who are virally suppressed between groups.

The analysis will include men who were on ART at enrollment.

This comparison is not protected by randomization therefore we will adjust for the following potential confounders:

- Age (in categories)
- Viral suppression at baseline
- Trimester of pregnancy at enrollment

30 Sep 2021

- Randomization arm
- Baseline covariates that demonstrate imbalance between the groups ($p < 0.05$ in comparison of characteristics), not thought to be mediators of differences in outcome.
- Assessments occurring prior to April 2020 (prior to COVID 19)

We will assess for effect modification by analysis of interaction between the subgroups of women who are virally suppressed at enrollment.

Handling of missing VL data:

- If 12 month VL is missing, but VL is available from 9 month PP, the 9 mo VL will be used to estimate the 12 mo VL.

7.3.5. Aim 2b. Assess whether having a male partner who has initiated PrEP/ART affects viral load suppression at 6 and/or 12 months post-partum in his female partner

Endpoint: Viral suppression at the 6 and 12 month visit post partum.

Statistical analysis:

Repeated measure analysis will be used for this aim. The viral load at 6 month and 12 months will use a time-dependent covariate for whether her male partner had initiated PrEP/ARV at least 3 months prior to the VL measurement. We will assess whether initiation of PrEP/ARV 3 month prior increases the probability of viral suppression using GEE logistic or modified Poisson regression

Handling of missing VL data:

- If 12 month VL is missing, but VL is available from 9 month PP, the 9 mo VL will be used to estimate the 12 mo VL.
- If 6 month VL is missing, but VL is available from 3 month PP, the 3 mo VL will be used to estimate the 6 mo VL.

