7.4. Secondary analyses

7.4.1. Aim 3: Evaluate associations between time of a women disclosing their HIV-infected status to their male partner and the trial endpoints: enrollment of the male partner, uptake of PrEP/ART; viral suppression

Descriptive analysis

- Tabulate the visit where the women first reported disclosure of her HIV-infected status to her partner
- For enrolled male partners, tabulate visit of first disclosure of male HIV status to his partner by male HIV status
- For women with enrolled partners, tabulate the joint disclosure of each partner by the end of the study

Statistical analysis

30 Sep 2021

- 1) Assess whether a woman's disclosure of HIV-infected status to her partner changes the probability of her male partner testing

Method: Time to event (event = male partner enrollment) Cox PH model with time varying covariate of women's disclosure. Disclosure is assessed as a cumulative time varying covariate, where a woman is considered disclosed if she self-reports disclosure at any time at or before the outcome is reported (i.e. if she reports disclosure at a visit before or at when her partner is enrolled). Women are assumed undisclosed until first visit she reports disclosure. Time is censored at the earliest of male partner testing (i.e. enrollment) or woman's last attended visit.

- 2) Assess whether male partner testing changes the probability of disclosure

Method: Time to event (event = woman's first report of disclosure) Cox PH model with time varying covariate of male partner enrolled. Women who self-report disclosure at baseline are excluded. Time is censored at the earliest of first disclosure or woman's last attended visit.

- 3) Assess whether a woman's disclosure of HIV-infected status to her partner changes the probability of initiation of PrEP/ART in her partner

Method: Same as 1) above, only with event = male partner initiated ART/PrEP. Analysis may be conducted in the entire v=cohort, and restricted to women with an enrolled partner

- 4) Assess whether a woman's disclosure of HIV-infected status to her partner changes VS of women

Method: Repeated measure analysis of outcome viral suppression in women. At each measurement of VL, primary time-varying covariate is whether the women has disclosed to her partner at or prior to the measurement. GEE model for probability of the outcomes will be used, including all visits where outcome is reported. Baseline viral loads are included

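### Disclosure of the woman's HIV status at enrolment is not a pre-specified covariate in Aim 2, and the SAP's mediator clause leaves it unclear whether it could enter the model

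*Protocol*

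**What the plan says.** **Protocol, Statistical considerations, Aim 2.** The inverse-probability weights are to use "potential time-varying confounders (Table 3), including sexual behavior, future fertility desires, relationship power dynamics, intimate partner violence, alcohol use, and baseline demographics", plus duration of ART before delivery. Disclosure is not named. The word that introduces the list leaves it open. The table it cites, Table 3, is the sample-size table. The behavioural-data table, Table 2, does not list disclosure either.

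**SAP 7.3.4 (Aim 2a).** "This comparison is not protected by randomization therefore we will adjust for the following potential confounders": age, baseline viral suppression, trimester, arm, and assessment before April 2020. One further item admits baseline covariates that differ between the groups at p<0.05, provided they are "not thought to be mediators of differences in outcome". Disclosure is not mentioned.

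**SAP 7.3.5 (Aim 2b).** No adjustment set is given.

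**What the SAP says about disclosure elsewhere:**
- 2.1.2: "As a women's HIV disclosure to her partner is hypothesized to be the mechanism for increasing her effective ART use"
- 5.2.2, among the key predictors: "Disclosure of HIV-infected status to male partner self-reported at baseline"
- 7.2, among the subgroups: "Women who have disclosed their HIV-infected status prior to/reported at baseline"
- 7.4.1, item 3: "Assess whether a woman's disclosure of HIV-infected status to her partner changes the probability of initiation of PrEP/ART in her partner"
- 7.4.1, item 4: "Assess whether a woman's disclosure of HIV-infected status to her partner changes VS of women"

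The protocol's Quantitative surveys section has disclosure asked of every woman at enrolment, so the variable will exist.

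**The concern.** A variable that may drive both exposure and outcome belongs in the adjustment set of a non-randomised comparison. The SAP treats disclosure as a candidate for both roles, yet no Aim 2 model is committed to using it.

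Women who had already disclosed at enrolment may be more likely to have a partner who comes forward and starts PrEP or ART, and more likely to be suppressed. If so, a model without disclosure credits the partner's treatment with a difference that was there before the study began. SAP 2.2.1 lists Aim 2a among the primary endpoints, so this would affect a headline result.

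The open slot in 7.3.4 is a weak safeguard. It depends on a significance screen, and disclosure is missing from the baseline lists in SAP 5.2.1 and 6.3.1, so it may never be screened. It also depends on the analyst judging that the variable the SAP calls the mechanism is not a mediator.

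**Working it through.** **1. The plan's own Aim 2 figures reproduce.** Exposed women = 500 × overall test uptake × [(1 − HIV prevalence) × 0.8 + prevalence × 0.5]. First row of protocol Table 4: uptake = (2 × 0.55 + 0.20)/3 = 0.433, and 500 × 0.433 × (0.6 × 0.8 + 0.4 × 0.5) = 500 × 0.433 × 0.68 = 147, as printed. Power is for a two-proportion test at two-sided 0.05 with 50% suppressed if unexposed, 1.75/2.75 = 63.6% if exposed, and 95% retention. It comes to 78.1% against the stated 78%. All eight power cells agree within 2 points. Table 4 is an unadjusted approximation, so it neither supports nor refutes this point.

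**2. Closed-form illustration.** Inputs from the documents: 147 exposed and 353 unexposed, 50% suppressed among the unexposed. Assumed, because the documents give no values: no true partner effect, 50% disclosed at enrolment, disclosure odds ratio 3 with exposure and 2 with suppression.
- Exposure probability overall is 147/500 = 0.294. An odds ratio of 3 gives 0.404 if disclosed and 0.184 if not.
- Share disclosed: exposed 0.5 × 0.404/0.294 = 0.687; unexposed 0.5 × 0.596/0.706 = 0.422.
- Suppression: 0.599 if disclosed and 0.428 if not, since 0.422 × 0.599 + 0.578 × 0.428 = 0.50.
- Apparent suppression if exposed: 0.687 × 0.599 + 0.313 × 0.428 = 0.545.
- Spurious RR = 0.545/0.50 = 1.09; spurious OR = (0.545/0.455)/1 = 1.20; chance of p<0.05 about 15%.

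Other assumptions, no true effect, 30-70% disclosed, 50% suppressed if unexposed:

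| Disclosure OR with exposure / outcome | Apparent OR | Type I error |
|---|---|---|
| 1.5 / 1.5 | 1.03-1.04 | about 5-6% |
| 2 / 2 | 1.10-1.12 | about 8-9% |
| 3 / 3 | 1.24-1.33 | about 19-30% |
| 5 / 3 | 1.34-1.50 | about 31-53% |

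**3. Simulation with the SAP's type of model.** Modified Poisson regression with robust standard errors, adjusted for baseline suppression and arm; 475 women (500 × 0.95) randomised 2:1; partner uptake of 30% × 0.68 and 55% × 0.68 by arm; no true effect. Assumed: 30-50% disclosed, odds ratio 2-4 for uptake and 2-3 for suppression, 50% suppressed at baseline with odds ratio 2 for later suppression.

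| Handling of disclosure | 50% suppressed at 12 months | 85% suppressed (assumed) |
|---|---|---|
| Left out | RR about 1.05-1.18; type I error about 9-44% | RR about 1.01-1.05; about 9-23% |
| Always adjusted for | RR about 1.00; about 4-7% | RR about 1.00; about 4-7% |

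The error rates move by a few points between runs.

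If disclosure is screened at p<0.05, it enters in 88-100% of trials at uptake odds ratios of 2 or more. RR is then 0.99-1.01 and type I error about 4-7%. At an uptake odds ratio of 1.5 it enters in only about 42-53%, but RR is then at most 1.02 and type I error 5-7%.

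**4. How strong would disclosure have to be?** The protocol's target OR of 1.75 is an RR of 0.636/0.50 = 1.27. To explain that away entirely, disclosure would need a risk ratio of about 1.27 + √(1.27 × 0.27) = 1.86 with both exposure and outcome (the E-value).

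**The case against.** Three stronger readings are tempting, and the documents support none of them.

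*That the SAP bars disclosure.* It does not. The mediator clause names no variable and qualifies only the imbalance slot. The mechanism sentence in 2.1.2 goes on to refer to the visit at which disclosure was first reported, which is a time-varying measure. An analyst could reasonably conclude that disclosure already made at enrolment is not a mediator and admit it. The simulation shows that this would remove the bias. What stands is that the text permits either reading.

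*That the Aim 2 estimate is confounded.* The items in SAP 7.4.1 are questions to be tested, using cumulative disclosure over time. Item 2 tests the reverse direction, from partner testing to disclosure. No prevalence or association is reported. Adjustment for baseline suppression may absorb part of any effect. So may the protocol's relationship-power and partner-violence terms, although these are not in the SAP's fixed list. Residual confounding is possible, not shown.

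*That disclosure at enrolment cannot be a mediator.* This holds for PrEP or ART started during the study. But 7.3.4 includes men already on ART at enrolment, and for those couples the order of disclosure and treatment is unknown.

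It is also fair to say that disclosure was not overlooked: it is a key predictor, a subgroup and the subject of its own secondary analyses. None of these puts it in the Aim 2 models.

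**Conclusion.** The point holds as a gap in pre-specification. Disclosure at enrolment is collected from every woman and hypothesised by the SAP to act on both exposure and outcome, yet it is a named covariate in neither Aim 2a nor Aim 2b. Its only way into Aim 2a depends on a p-value screen and an ambiguous clause.

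The consequence is conditional. If disclosure is left out and is associated with both partner uptake and suppression at odds ratios of 2 or more, a null partner effect would be reported as a modest benefit too often: up to about RR 1.18 and 44% type I error at the protocol's 50% suppression, and up to about RR 1.05 and 23% at 85%. If the associations are near 1.5, or if disclosure is adjusted for by either route, the bias is negligible. The direction toward benefit assumes that disclosure raises both uptake and suppression. These sizes rest on assumed disclosure inputs and are not estimates for this trial.

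**What to change.** 1. In SAP 7.3.4, add disclosure of HIV status to the partner, as reported at enrolment (yes/no), to the fixed covariates. Use the same term in 7.3.5.
2. State that, for disclosure, the mediator exclusion applies only to disclosure first reported after enrolment.
3. In the protocol's weight model, name disclosure reported before the exposure visit as a time-varying confounder, and correct the reference to Table 3.
4. Because the order is unknown for men already on ART at enrolment, repeat Aim 2a without those couples as a sensitivity analysis.

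The cost is SAP wording, one degree of freedom and one extra model run. No new data are needed, and no stated power figure changes.
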